## 2.3 RISK/BENEFIT ASSESSMENT

### 2.3.1 KNOWN POTENTIAL RISKS

The study presents no more than minimal risk of harm to human subjects. There are no long-term risks to subjects related to the procedures described in the protocol. Immediate risks to subjects may include:

- The loss of privacy and confidentiality.
- Some aspects of the assessments (e.g. completing the questionnaires) may be uncomfortable because of questions regarding health habits and demographics.
- Possible discomfort wearing the virtual reality headset.
- Fatigue and injury related to the text message program.

### 2.3.2 KNOWN POTENTIAL BENEFITS

Based on the NIH Behavioral and Social Intervention Clinical Trial Protocol Template v3.0 - 20180827

Immediate potential benefits to subjects include:

- Regardless of motivation to quit, participants will receive information about local and national smoking cessation resources (online resources, tobacco cessation quitline, clinic-based programs, and text message programs). The information can be acted upon immediately or when the participant is ready to quit smoking.

---

### 2.3.3 ASSESSMENT OF POTENTIAL RISKS AND BENEFITS

Although this study poses no more than minimal risk of harm to subjects, potential risks include loss of confidentiality, discomfort wearing the VR headset, and participants may feel uncomfortable answering some questionnaire items.

To minimize risk of loss of confidentiality, study data, documents, case report forms (CRFs), and other documents and files will be identified with a unique study ID number. The study ID number will be linked to a mastercode list that contains all study ID numbers and direct subject identifiers (e.g., name, address, telephone number, etc.). The mastercode list will be maintained in a secure, protected and HIPAA compliant drive separately from other study files, and access will be limited to members of the research team. Additionally, study data will be collected electronically using tablets or laptops through secure web-based application software REDCap managed by the Boston University Biostatistics and Epidemiology Data Analytics Center (BEDAC) at the Boston University (BU) School of Public Health. Electronic CRFs (eCRFs), provide for consistent data collection within the REDCap study management system. Data will be securely stored according to BU policy. Electronic devices for data collection (e.g., tablets or laptops) are password protected and kept in a locked filing cabinet when not being used. Data collected from research participants will be stored in a secured, password-protected computer file that is separate from identifiers. Any paper data will be placed in a locked file cabinet. Participant information will be accessible only to research staff. All research data, including a copy of the mastercode, will be kept for 7 years after completion of the project to allow for reidentification in case of an audit or other review, and in compliance with BU policy #FA-002.

“Agile Health” (AH) is the company that will be programming and delivering our 4-week text message curriculum. Their database will contain the text messages including information on what text messages each participant has received, which texts participants have responded to, their actual responses, and feedback about individual messages. This database is HIPAA secure. Agile Health will not have access to the link between participant contact information and survey data. To ensure the highest level of data confidentiality, secure data transfer will occur through REDCap managed by the Boston University Biostatistics and Epidemiology Data Analytics Center (BEDAC) at the School of Public Health. Following a discussion with the BU director of health privacy and compliance, a BAA for this study is not required. Following a discussion with BUMC Information Security, study's co-investigator [name] is the appointed coordinator who will conduct quarterly access audits in consultation with Agile Health.

In order to verify that study participant have connected with the quitline, we need to share subject identifiers with National Jewish Health, which is the contracted vendor for the Massachusetts State quitline. The participants' information we share includes: 1) participant's name, 2) participant's telephone number, 3) participant's date of birth, and 4) participant's home address. We will also need to share the study enrollment date.

These identifiers constitute the minimum necessary data requested by National Jewish Health to enable them to verify in their database:

1. whether the participant made contact with the quitline; 2. whether the participant elected to start counseling; 3. the type of counseling the participant requested (e.g., phone, web or text message); 4. the number of counseling session the participant received; 5. whether the participant set a date to quit smoking; 6. whether the participant requested nicotine replacement products; and 7. whether nicotine replacement products were sent to the participant. Data sharing between the study team and National Jewish Health will only occur through a secure encrypted email system.

It is possible that some aspects of the assessments (e.g., answering questions about health habits and demographics) may be uncomfortable for some participants. However, participants will be informed that they may choose not to answer any questions that make them uncomfortable.

Participants will watch the videos through a VR headset during their teeth cleaning. The VR headset we used during the UG3 usability study (Viotek Spectre) was rated highly comfortable by participants. However, if a participant feels uncomfortable wearing the headset during the video, he or she may remove it. In this case, we will terminate participation and compensate the participant accordingly.

There are two potential risks of text messaging: accidents, thumb, and joint pain. Frequent texting may increase the risk of thumb and joint pain. The number of texts involved in this study is not likely to result in thumb and joint pain. To prevent text message-related injury, we will inform participants that text messages should not be attended to while driving or walking. In a previous pilot study that included a similar text message curriculum participants received for two months, there were no issues related to fatigue interacting with text messages, and the text message program was well received by participants.

### 3 OBJECTIVES AND ENDPOINTS

OBJECTIVES	ENDPOINTS	JUSTIFICATION FOR ENDPOINTS	PUTATIVE MECHANISMS OF ACTION
Primary			
To test the efficacy of the Intervention vs. Controls in increasing contact with, and utilization of, EBTs over a 7-month study period.	
 
-Any EBT contact over the 7-month study period.
 
-Total number of EBTs contacted – ranging 0 to 4 – over the 7-month study period
 
-EBT utilization index score over the 7-month study period
 
	Because effective cessation programs already exist, innovations are needed to drive smokers to engage with them. 40-80% of smokers are not ready to quit within 30 days, and efforts are needed to reach smokers with motivational interventions in their natural settings. Because we are proactively reaching patients, they may or may not be ready to quit smoking. Therefore, quit rates would be expected to be low if we were focusing on cessation, necessitating a very large sample to be able to compute power. The goal of the study is to test whether a clinic-based intervention that reduces provider burden and has minimal patient burden can drive patients to make contact with EBTs. Our prior research has shown that smokers who are not motivated to quit either lack knowledge about the EBTs, do not know how to access EBTs, and/or have myths about EBTs. The video-based intervention and subsequent 4-week text message program addresses these barriers, and provides motivational strategies to make contact with EBTs.	The VR video intervention including the subsequent 4-week text message program target social cognitive theory constructs (e.g., motivation, self-efficacy, outcome expectations) which are the hypothesized mechanisms that mediate the effect of the intervention on the primary study endpoints.
Secondary			
To test the efficacy of the Intervention vs. Controls in motivating smokers to use a combination of medication and counseling.	-Combination of at least one form of counseling EBTs (state quitline counseling, clinic-based counseling, text messaging) and at least one form of medication (nicotine replacement	Participants may utilize more than one EBT and will be encouraged to do so. Evidence shows that a combination of counseling and medication is more effective than either treatment alone.	

OBJECTIVES	ENDPOINTS	JUSTIFICATION FOR ENDPOINTS	PUTATIVE MECHANISMS OF ACTION
	therapy or tablet medication) over the 7-month study period.		
To test the efficacy of the Intervention vs. Controls on quit attempts and on motivation to quit.	
-The number of quit smoking attempts, since last contact, that lasted 24 hours or more, not due to hospitalization or illness over the 7-month study period.
 
-Participants' motivation to quit smoking within 30-days over the 7-month study period.
	Quit attempts and motivation to quit are robust interim predictors of smoking cessation. 	
To test the efficacy of the Intervention vs. Controls on biochemically verified smoking abstinence.	-Biochemically verified 7-day point prevalence abstinence as indexed by salivary cotinine level < 15 ng/mL measured at 1- 3- and 6-months post treatment	Biochemically confirmed self-report of 7-day point prevalence abstinence is best practice in smoking cessation induction clinical trials. 	

OBJECTIVES	ENDPOINTS	JUSTIFICATION FOR ENDPOINTS	PUTATIVE MECHANISMS OF ACTION
To assess the mechanisms through which the intervention effects occur (mediators) and to identify subpopulations for whom intervention effects differ (moderators)	
-Mediators include the social cognitive theory constructs of motivation, self-efficacy, outcome expectations, measured over the 7-month study period.
 
-Moderators include perceived stress, readiness to quit smoking, gender and race/ethnicity.
	
-Social cognitive theory's theoretical constructs are the hypothesized mechanisms of action (targeted by the intervention) that mediate the effect of the intervention on study's endpoints.
 
-The role of moderators will be exploratory.
	

## 4 STUDY DESIGN

### 4.1 OVERALL DESIGN

This study is a 2-arm, stage III randomized controlled efficacy trial. Three hundred seventy-six patients will be recruited at Boston University GSDM patient treatment center or TU comprehensive care (or Periodontal) clinic, and randomized to the Intervention group or the Control group. To account for participants who become ineligible post-informed consent (e.g., do not complete baseline activities, do not show up to dental visit) and thus are not randomized, we estimate that approximately 700 subjects will be enrolled. Our aim is to test whether the Intervention administered to dental patients during teeth cleaning increases contact with, and utilization of, EBTs. Smokers randomized to the Intervention group will receive: 1) the smoking cessation video intervention via VR headset during their teeth cleaning, 2) brochure about EBTs, and 3) 4-weeks of tailored, interactive, and automated text messages to motivate engagement with EBTs plus periodic text message reminders throughout the study. The Control group will watch a relaxation video through the VR headset during their teeth cleaning, receive a brochure about EBTs, and receive assessment-only text messages. We chose a 'relaxation video' because this topic is at least somewhat connected to the teeth cleaning experience (e.g., to ease dental anxiety and discomfort), rather than watching a video on general health and wellness, for example.

The Primary Objective is to test the efficacy of the Intervention vs. Controls in increasing contact with, and utilization of, EBTs over a 7-month period. Hypothesis 1.1 states: Participants randomized to the Intervention will be more likely to engage (make contact with) EBTs. Hypothesis 1.2 states: Participants randomized to the Intervention will have greater EBT utilization (e.g., more quitline counseling sessions, more days in the text message program).

The Secondary Objectives are: 1) To test the effect of the Intervention vs. Controls on quit attempts and on motivation to quit. Hypothesis 2 states: Participants in the Intervention will make more quit

Based on the NIH Behavioral and Social Intervention Clinical Trial Protocol Template v3.0 - 20180827

attempts and increase their motivation to quit; 2) To test the efficacy of the Intervention vs. Controls on biochemically verified smoking abstinence. Hypothesis 3 states: Participants in the Intervention will achieve higher rates of point-prevalence abstinence at follow-up; 3) To assess the mechanisms through which intervention effects occur (mediators such as self-efficacy, motivation, and outcome expectations) and to identify subpopulations for whom intervention effects differ (moderators such as gender and motivation to quit). Hypothesis 4 states: The Intervention will directly affect the putative mediators of intervention effect, which will in turn affect EBT engagement (contact) and utilization. The role of moderators will be exploratory.

Participants will be randomized (1:1) at the dental clinic, after receiving the study brochure and before watching the videos during their teeth cleaning. Randomization will be implemented by employing a stratified block procedure with small, random size blocks and will be stratified by motivation to quit (ready to quit smoking in 30 days vs. not ready to quit within 30 days). To avoid randomization errors, randomization will be configured within REDCap, the secure web application used to build and manage the questionnaires and study forms which is programmed and managed by the BU Biostatistics and Epidemiology Data Analytics Center (BEDAC). A biostatistician will build the randomization program. The study RA will trigger randomization by pressing the feature on the REDCap eCRF form using an iPad. All dental providers will be masked to treatment condition because both the Intervention group and the Control group will be watching a video through the VR headset. Only the PI, project director, statistician, and study RA who is in the clinic will be unmasked to treatment condition.

At the teeth cleaning appointment, all participants will receive a Viotek Spectre virtual reality and earbuds with volume control. A study smartphone (iPhone) will be inserted into the headset and programmed to show either the intervention or the control video, depending upon the patient's randomization. Both videos will be the same duration (10 minutes). Participants randomized to the Intervention group will watch one of two videos dependent upon their latest assessment of motivation to quit (assessed at the dental clinic appointment). If the participant is motivated to quit within 30 days, they will watch the "Ready to Quit" video; those not motivated to quit within 30 days will watch the "Not Ready to Quit" video. The RA will help the participant adjust the headset for comfort and use the audio control on the earbuds to ensure the volume is set at a level where the participant is able to hear the practitioner while watching the video. Participants will be advised to raise their hand to signal for adjustments, removal of the headset, or the conclusion of the video.

Shortly after participants complete watching the assigned video, the RA will trigger the post-video questionnaire in REDCap. The post-video questionnaire will be delivered as e-link through text message and email to all participants. Participants will be required to complete this questionnaire in their own time within 10 days of receiving the e-link invitation.

Within 24 hours of randomization, the Intervention group will begin the 4-week text message curriculum program that has been designed in preparatory research to: a) motivate EBT contact and utilization, b) facilitate transition to EBTs, c) dispel myths and misinformation about EBTs, and d) measure mediators weekly. There are two different tracks of text messages to motivate EBT contact and utilization: one for those who are motivated to quit and one those who are not motivated to quit. The Control group will receive assessment-only text messages, and will follow the same schedule as the assessment text messages in the intervention group (e.g., one text message to assess motivation, one to assess self-efficacy, and one to assess outcome expectancies each week for three weeks). All participants will be able to connect to, and access the services of, one or more EBT resources at any point during the study: both groups receive this information at the dental clinic visit via brochure, and the Intervention group

will receive additional information via text messaging. At the conclusion of both text message programs (Intervention text messages and Control group assessment-only text messages), participants will complete an end-of-treatment assessment (*Time 4*, immediately after the end of the text message program 4-weeks post-randomization). Follow-up assessments will occur at *Time 5* (3-months post end-of-treatment assessment), and at *Time 6* (6-months post end-of-treatment assessment). Participants who self-report quitting smoking at any of these assessments will be asked to provide a saliva sample for biochemical verification of smoking abstinence. Samples will be assayed for cotinine; smoking abstinence is defined as cotinine values < 15 ng/mL.

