## 1 PROTOCOL SUMMARY

### 1.1 SYNOPSIS

Title:	A Smoking Cessation Induction Intervention Via Virtual Reality Headset During a Dental Cleaning: Randomized Controlled Trial
Grant Number:	1UG3DE028866
Study Description:	
The primary aim of the UH3 Stage III randomized efficacy trial is to test whether a video-based smoking cessation induction intervention delivered via virtual reality (VR) headset during part of a dental hygiene appointment increases dental patients' utilization of evidence-based treatments (EBTs) for smoking cessation (Massachusetts State quitline, clinic-based programs, NCI text message program [SmokefreeTXT], nicotine replacement products or other smoking cessation medications) within 7-months post-dental hygiene appointment. 437 cigarette smokers scheduled for dental prophylaxis or scaling and root planing at the Boston University Goldman School of Dental Medicine (BUGSDM) patient treatment center or Tufts University (TU) School of Dental Medicine Comprehensive Care Clinic or Periodontal Clinic will be randomized (1:1) to either the Intervention (smoking cessation video via VR headset, brochure about EBTs, and four-week of interactive, automated and tailored text message program to motivate EBT utilization) or Control group (control video on relaxation via VR headset, brochure about EBTs, and assessment-only text messages). The primary hypotheses are: Hypothesis 1.1: Participants in the Intervention will be more likely to contact and engage with EBTs and Hypothesis 1.2: Participants in the Intervention will have greater EBT utilization. The secondary hypotheses are: Hypothesis 2: Participants in the Intervention will have greater quit attempts and motivation to quit. Hypothesis 3: Participants in the Intervention will achieve higher biochemically confirmed smoking cessation rates at follow-up. Hypothesis 4: The Intervention will directly affect the putative mediators of intervention effect, which will in turn affect EBT utilization. The role of moderators will be exploratory.

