**Study Population:**

Secondary Endpoints: Quit smoking attempts, motivation to quit smoking, and biochemically verified smoking abstinence (7-day point prevalence).

Exploratory Endpoints: Use of a combination of medications and counseling; mediators of the intervention effect, and moderators. Participants will be 437 men and women ( $\geq 18$  years of age) who are patients at Boston University GSDM pre-doctoral, or post-doctoral periodontal, treatment center, or TU Comprehensive Care Clinic or Periodontal Clinic, and smoke cigarettes, and are scheduled for dental prophylaxis or scaling and root planing at either dental clinic. The GSDM pre-doctoral and post-doctoral periodontal treatment centers are located in Boston, Massachusetts. Equal numbers of males and females receive treatment at the clinic, the average age is 46 years, and 25% are uninsured. Pilot data showed that, among smokers attending the clinic, 74% were unemployed and 57% were from minority groups.

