Rationale for Study Design and Innovation. Previous studies of smoking cessation in dental settings have relied on provider-based counseling, which can be costly in terms of provider training time, time spent delivering the intervention, and monitoring ongoing treatment fidelity. Prior studies suffer from dissipation of treatment effects over time; lack of objective verification of major outcome variables; recruiting only smokers who are ready to quit; and lack of "Arranging follow-up" as recommended by the NCI 5 As. Furthermore, few studies have specifically targeted settings that serve urban and low income smokers. The proposed study will fill in the gaps by: 1) testing the intervention in a fully powered, longitudinal trial, 2) using objective measurement for primary outcomes and for smoking cessation, 3) delivering an intervention that has minimal provider and patient burden, increasing the likelihood that it will be disseminated, 4) using a novel method of delivering an intervention while clinical care is being provided and without a loss of treatment fidelity, 5) targeting all smokers—not only those who are ready to quit, and 6) testing mechanisms of change. This study attempts to bridge the gap between dentistry and cessation services.

Study Design: The aim of the study is to test whether a video-based smoking cessation induction intervention delivered through a VR headset during dental cleanings increases utilization of EBTs for smoking cessation. Specifically, we will assess utilization of the following EBTs: the Massachusetts State quitline (operated by National Jewish Health), clinic-based programs (e.g., community health centers, hospital smoking cessation clinics), National Cancer institute's (NCI) text message program (SmokefreeTXT), nicotine replacement therapy (NRT) products, and non-NRT smoking cessation medications. 437 smokers will be randomized to either the Intervention consisting of: 1) smoking

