## 9.2 SAMPLE SIZE DETERMINATION

Power calculations focus on the comparison of those randomized to the Intervention vs. Control on our primary outcome of any EBT engagement through a chi-square test at the two-sided  $\alpha = 0.05$  level. We will not adjust p-values for multiple comparisons.

Using the odds ratio as our effect size, we estimate the effect of the Intervention will be  $OR=2.05$  (corresponding to percent with any EBT utilization of 22.7% in the Control vs. 37.6% in the Intervention). Only two published studies tested the efficacy of an intervention on EBT utilization rate, both at 12-months follow-up. Brooks et al reported an EBT utilization rate (i.e., Quitline or clinic-based program) of 29.8% in the intervention group vs. 14.7% in controls ( $OR=2.4$ ). Fu et al reported an EBT utilization rate (counseling or medications) of 44.2% in the intervention and 30.6% in controls ( $OR=1.8$ ). Therefore, we use the average EBT utilization rate in the control groups from these studies (22.7%) as our ‘any EBT utilization’ rate under the null hypothesis in the power analysis. Because neither of the above studies used video or were conducted in a dental setting, we also considered previous studies testing the effectiveness of videos on cessation, which report ORs of 1.9 and 3.0, and previous studies on cessation in dental settings (meta-analysis  $OR=2.38$ ). Based on all the above, we conservatively chose an anticipated effect size of  $OR=2.05$  (corresponding to rates of 22.7% vs. 37.6%). With  $\alpha=0.05$  (two-sided), we need a total sample of  $n=300$  subjects to achieve 0.80 power of detecting this anticipated effect. However, because of potential differences between clinic sites, and assuming an attrition rate of 20% (lost to follow-up or ineligible post-randomization), in consultation with the NIDCR in April 2024 we received authorization to increase the sample size to  $n=455$  subjects ( $n=227$  for intervention and  $n=228$  for control group). Therefore, with  $\alpha=0.05$ , the anticipated effect size of  $OR=2.05$ , and 364 subjects (455 minus 20% lost to follow-up or ineligible post-randomization), we will have 0.87 power to detect the anticipated effect.

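### The current text gives three randomisation targets (376, 437 and 455); the 376 in section 4.1 gives power of about 0.81, not the 0.87 stated in section 9.2

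*Combined protocol and SAP*

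**What the plan says.** All of these statements are current body text in the combined protocol and SAP.

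- **Section 4.1, Overall Design:** "Three hundred seventy-six patients will be recruited at Boston University GSDM patient treatment center". The sentence goes on to name the Tufts clinic as the alternative site and says that these patients are randomised to the two groups. The next sentence allows for people who consent but are never randomised: "we estimate that approximately 700 subjects will be enrolled".
- **Section 1.1, Synopsis, Study Description:** "437 cigarette smokers scheduled for dental prophylaxis or scaling and root planing", to be randomised 1:1. Under Study Population: "Participants will be 437 men and women".
- **Section 2.1, Study Rationale:** "437 smokers will be randomized to either the Intervention consisting of".
- **Section 9.2, Sample Size Determination:** "in consultation with the NIDCR in April 2024 we received authorization to increase the sample size to" 455, split 227 and 228. The power statement follows: "364 subjects (455 minus 20% lost to follow-up or ineligible post-randomization), we will have 0.87 power to detect the anticipated effect". The same section says that a total of 300 is needed for 0.80 power at the same effect.

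No section states an expected proportion of consented patients who go on to be randomised.

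**The concern.** The number to be randomised should have one value, and here it has three, spanning 455 − 376 = 79 participants. The 376 in section 4.1 cannot be read as a target for one site before the second was added, because the same sentence names both sites. It is not presented as history either. The conflict lies within the current text and does not depend on the summary of changes.

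Two things are at stake. First, the 0.87 in section 9.2 describes the trial only if recruitment runs to the number on which it was calculated. Staff working from section 4.1 would stop at a smaller one. Section 7.2 also allows some randomised participants to be replaced, which presupposes a known total. Second, the enrolment estimate appears only next to the smallest target, so it is unclear whether it still supports recruitment to the larger ones.

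**Working it through.** **Inputs, all from section 9.2 unless stated.** Control rate p1 = 0.227; intervention rate p2 = 0.376; two-sided alpha 0.05 by chi-square test; attrition 20%; 1:1 allocation (sections 1.1 and 4.1); targets 376, 437 and 455.

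**Formula.** With n evaluable per arm and p̄ = (p1 + p2)/2 = 0.3015:

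power = Φ{ [ |p2 − p1| − 1.96·√(2p̄(1 − p̄)/n) ] / √( (p1(1 − p1) + p2(1 − p2))/n ) }

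Here |p2 − p1| = 0.149, 2p̄(1 − p̄) = 0.4212, and p1(1 − p1) + p2(1 − p2) = 0.1755 + 0.2346 = 0.4101.

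**Step 1: reproduce the plan's own figures.**
- Odds ratio: (0.376/0.624)/(0.227/0.773) = 2.05, as stated.
- Total of 300 (150 per arm): power 0.806, against the stated 0.80. The formula asks for 148 per arm, 296 in all.
- 455 × 0.8 = 364, so n = 182. The null standard error is √(0.4212/182) = 0.0481 and the alternative standard error is √(0.4101/182) = 0.0475. Then (0.149 − 1.96 × 0.0481)/0.0475 ≈ 1.153, and Φ(1.153) ≈ 0.8755. The stated 0.87 is within one point.

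The calculation in 9.2 is therefore sound for the number attached to it.

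**Step 2: apply the same method and the same attrition to each target.**

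| Randomised | Where stated | Evaluable at 80% | Power | Difference from 0.87 |
|---|---|---|---|---|
| 455 | 9.2 | 364.0 | 0.8755 | +0.006 |
| 437 | 1.1, 2.1 | 349.6 | 0.862 | −0.008 |
| 376 | 4.1 | 300.8 | 0.807 | −0.063 |

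The 376 row matches a design that needs 300 evaluable: 300/0.8 = 375. That fits the requirement in 9.2 before the authorised increase, but this link is an inference.

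**Step 3: sensitivity to the test formula.** At 455, 437 and 376 respectively, after attrition:
- unpooled: 0.881, 0.868, 0.814
- arcsine: 0.877, 0.864, 0.809
- continuity-corrected: 0.850, 0.834, 0.770

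The ordering and the gap persist. The continuity-corrected version is not the plan's method, since it gives 0.769 at 300 where the plan states 0.80.

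**Step 4: the enrolment estimate.** Against 700 enrolled, the implied share randomised is 376/700 = 53.7%, 437/700 = 62.4% or 455/700 = 65.0%. If the 376/700 share held, which is an assumption and not a figure in the documents, 437 would need 437/0.537 ≈ 814 enrolled and 455 would need 455/0.537 ≈ 847.

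**The case against.** The strongest reply is that section 9.2 settles the matter. It alone gives arm sizes, a reason for the increase, an authorisation and a power calculation, so 376 and 437 look like numbers that were not carried forward. That is probably the right reading, and it is why 455 is the natural figure to adopt. It does not remove the contradiction, because section 4.1 states the design in the present tense with a different total.

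Several stronger readings are tempting, and the documents do not support them:

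- **That 0.87 fails at two of the three targets.** At 437 the power is 0.862, less than one point below the stated figure. Only 376 falls materially short.
- **That the trial would be underpowered.** By the plan's own standard of 300 evaluable for 0.80 power, even 376 suffices: about 301 evaluable and power 0.81.
- **That 700 fits only 376.** It exceeds all three targets, and with no stated yield a share of 62% or 65% cannot be ruled out. It is also called an estimate. The text sets no ceiling on consent.
- **That the arithmetic in 9.2 is wrong.** It reproduces.
- **That the 1.2 schema is also inconsistent.** The figure is not visible in the text available here, so this can only be checked, not asserted.

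**Conclusion.** The point stands as an internal inconsistency in the trial's sample size. Three totals are in force for the same two-site trial. The practical consequence attaches to one of them: recruiting only to the 376 of section 4.1 would give power of about 0.81, some 6 points below the 0.87 claimed, though still above 0.80. The choice between 437 and 455 hardly affects power.

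These figures assume the event rates, alpha and 20% attrition of section 9.2, applied equally at each target, and a chi-square test without continuity correction. On enrolment, the supportable statement is narrower: about 700 is given beside 376, and the documents do not show that it was re-derived for 437 or 455. The documents do not say how many have been randomised, so whether the discrepancy could still affect recruitment is not known from them.

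**What to change.** 1. State one randomisation target in sections 1.1 (Study Description and Study Population), 2.1, 4.1 and 9.2, and check that the schema in 1.2 agrees. On the present text that target is 455, the only figure described as authorised and the one on which the power rests.
2. If a different target is intended, restate the power in 9.2: about 0.86 for 437 or about 0.81 for 376, with the evaluable number changed to match (about 350 or 301).
3. In section 4.1, confirm or restate the expected number enrolled and give the assumed share of consented patients who will be randomised. The figure of about 847 for 455 applies only if the 376/700 share is the sponsor's expectation. Observed yield to date, if available, would be a better basis.

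The cost is a handful of text corrections in the next amendment, with whatever IRB review such an amendment needs. No analysis or design element changes if 455 is confirmed.
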